5.4.5 Prohibited Concomitant Therapies

The following therapies are prohibited because they may interfere with the efficacy and/or safety assessment of the study products:

- Botulinum toxin of any serotype.
- Any other investigational new drug or device.
- Any absorbable (temporary) or non-absorbable (permanent) material in the treatment areas.
- Facial aesthetic procedures (e.g., ablative skin resurfacing, laser treatment, micro needling, photodynamic therapy, tattooing or chemical peel) or any other procedures in the treatment area.
- Facial surgery or eye surgery (including LASIK procedure).
- Medications that affect neuromuscular transmission such as curare-like depolarizing agents, lincosamides, polymyxins, anticholinesterases and aminoglycoside antibiotics.

If a prohibited therapy becomes a necessary treatment for best clinical interest of the subject or due to safety reason, the Medical Monitor (Section 11.9) should be notified, if time permits, to discuss possible alternatives prior to administration of a prohibited therapy.

If a subject receives a prohibited therapy during the clinical study, the Medical Monitor (Section 11.9) should be notified to discuss the subject's continuation in the clinical study.

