9.1.2 Populations Analyzed and Evaluability

The statistical analyses will be performed based on the following subject populations.

9.1.2.1 *Modified Intent-to-treat (mITT) Efficacy Population*

The modified Intention-to-treat (ITT) population includes all subjects who are randomized and dispensed the investigational product, and will be analyzed according to the randomization scheme; subjects with a photographic and categorical scale Month 1 assessment via a remote visit will be excluded from the mITT. The mITT population will be used for primary efficacy analysis.

 GALDERMA	Title 43QMI902 Clinical Study Protocol - QM1114 - LCL and GL	Doc id MA-40371
--	---	----------------------------------

Effective date: 2020-06-09 07:02

Effective

Version: 4.0

9.1.2.2 *Intent-to-treat (ITT) Efficacy Population*

The Intention-to-treat (ITT) population includes all subjects who are randomized and dispensed the investigational product, and will be analyzed according to the randomization scheme. All secondary efficacy **CCI** variables will be analyzed based on the ITT population, as well as a sensitivity analysis of the primary efficacy endpoint.

9.1.2.3 *Per-protocol (PP) Efficacy Population*

The Per Protocol (PP) population is a subset of the mITT subjects who have no protocol deviations that are considered to have a substantial impact on the primary efficacy outcome. If the PP population contains less than 90% of the subjects in mITT, a sensitivity analysis of the primary efficacy endpoint will be performed based on the PP population.

9.1.2.4 *Safety Population*

The safety population includes all subjects who were administered the study product, and will be analyzed according to as-treated principle. All safety data will be summarized descriptively based on the safety population.

9.1.2.5 *Imputation of Missing Data*

The Observed Cases (OC) will be used for all safety analyses as well as the secondary **CCI** efficacy analyses. The primary efficacy analysis will be performed using multiple imputation (MI) and repeated using baseline observation carried forward (BOCF) for missing values. If deemed necessary, any analyses may be repeated using OC, BOCF, or MI as appropriate.

9.1.3 *Data Presentation and Graphics*

All statistical analyses, including summary tables and data listings, will be performed using the SAS® system (version 9).

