1.4.2 Secondary efficacy endpoints

Secondary endpoints include:

- (i) Percentage of subjects who achieve a score of 0 or 1 at each post-treatment visit using the GL-ILA at maximum frown
- (ii) Percentage of subjects who achieve a score of 0 or 1 at the same visit for both left and right sides summarized for each post-treatment visit using the LCL-ILA at maximum smile

CCI

 GALDERMA	<small>Title</small> 43QMI902 Statistical Analysis Plan US - QMI114-DP - GL&LCL	<small>Doc id</small> MA-43265
---	--	-----------------------------------

Effective date: 2021-02-05 13:16

Effective

Version: 1.0

CCI

 GALDERMA	<small>Title</small> 43QMI902 Statistical Analysis Plan US - QMI114-DP - GL&LCL	<small>Doc id</small> MA-43265
---	--	-----------------------------------

Effective date: 2021-02-05 13:16

Effective

Version: 1.0

[figure not shown]
CCI

Effective date: 2021-02-05 13:16

Effective

Version: 1.0

 GALDERMA	<small>Title</small> 43QMI902 Statistical Analysis Plan US - QMI114-DP - GL&LCL	<small>Doc id</small> MA-43265
---	--	-----------------------------------

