2.1 General methods

All tables, listings, and figures will be programmed using SAS Version 9.4 or higher. Data collected in this study will be documented using summary tables and subject data listings created by using the SAS® system. Confidence intervals (CI) and p-values will be 2-sided and performed at a significance level of 5%, unless otherwise specified. Data for all subjects in the clinical database will be included in the data listings. Calculated (derived) variables will be listed as appropriate. Any changes from the SAP will be detailed in the clinical study report.

All efficacy, safety and baseline characteristics variables will be presented using descriptive statistics within each treatment group, and graphs as appropriate. Continuous variables will be summarized using descriptive statistics (number of observations, mean, standard deviation [SD], median, minimum, and maximum). Categorical variables will be presented in frequency tables with number and percentage of observations for each level. Missing counts for all variables will be presented for informational purposes only and will not be included in percentage calculations.

Study days will be calculated relative to the injection of study drug. Day 0 will be the day of study drug administration. Baseline will be the last assessment prior to the injection of study drug unless otherwise indicated. The Screening Visit 1 (Day -14 to Day 0) will be considered the visit prior to injection of study drug. Because the Screening visit and Baseline visit (Day 0) may be performed on the same day, the Screening visit can also be Day 0.

Adverse events, cosmetic/aesthetic procedures and implant history events, medical history events, and concomitant treatments/procedures will be coded using MedDRA, Version 23.0.

Prior/concomitant medications and procedural anesthetics will be coded using the World Health Organization (WHO) Drug Dictionary Global, 1 Sep 2019 B3 or higher.

In general, efficacy, safety, **CCI** analyses will be performed and summarized by treatment group (QM1114-DP, placebo), unless otherwise stated.

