2.4.2 Handling of missing data

In general, the number of subjects with missing values will be summarized and reported as appropriate in all outputs. The primary analysis will be performed using multiple imputation (MI) as the primary imputation method and repeated using baseline observation carried forward (BOCF) as a sensitivity analysis for missing values. With the BOCF imputation method, if a subject is missing their Month 1 GL-ILA/GL-SLA scores or LCL-ILA/LCL-SLA Month 1 scores, their score at baseline will be used, respectively.

The imputation using MI will assume the Missing Completely at Random (MCAR) missing data assumption. Regardless of the actual pattern of missing data, the Markov Chain Monte Carlo (MCMC) method of the MI procedure from the SAS® system will first be used to create a monotonic pattern of missing data. Then, a second MI procedure will be used to generate five sets of data with missing values imputed from observed data. Linear regressions will be employed to model the missing GL-ILA, GL-SLA, left LCL-ILA, right LCL-ILA, left LCL-SLA, and right LCL-SLA scores separately, with the following covariates included in each imputation model: treatment group and non-missing ILA or SLA data, respectively for GL and LCL, from earlier timepoints (baseline, Day 7, and Day 14). The imputed datasets will be used to create the composite responder variable, which will then be analyzed using the methodology described for the primary analysis of responder rates at Month 1 ([Section 2.4.3](#)). The results from the analysis of the multiple imputed datasets will be combined by the MIANALYZE procedure of the SAS® system. The seed number to be used will be the number 110197.

The secondary efficacy analysis (described in [Section 2.4.4](#)) will be performed using the Observed Cases (OC), that is, no imputation will be done. **CCI**

	Title 43QMI902 Statistical Analysis Plan US - QM1114-DP - GL&LCL	Doc id MA-43265
--	---	----------------------------------

CCI

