2.4.4 Secondary analysis

To evaluate the effectiveness of a single dose of QM1114-DP in the LCL and QM1114-DP in the GL, alone or in combination, the GL-ILA at maximum frown and LCL-ILA at maximum smile responders at each visit will be presented in frequency tables. The respective responder rates (specified in [Section 1.4.2](#)) will be calculated and presented by treatment group and visit. Corresponding 95% CI for the GL-ILA at maximum frown and LCL-ILA at maximum smile responder rates will also be presented. The Clopper-Pearson (Exact) method will be used to calculate the CIs. The CMH analyses, as outlined in the Section 2.4.3, will be conducted for descriptive purposes.

The secondary analysis will be based on the ITT population with the remote visit assessments excluded. A sensitivity analysis will be conducted using the ITT population including the remote visit assessments.

The above responder rates will be presented in figures by visit and treatment group.

Effective date: 2021-02-05 13:16

Effective

Version: 1.0

 GALDERMA	<small>Title</small> 43QMI902 Statistical Analysis Plan US - QMI114-DP - GL&LCL	<small>Doc id</small> MA-43265
---	--	-----------------------------------

CCI

 GALDERMA	Title 43QMI902 Statistical Analysis Plan US - QM1114-DP - GL&LCL	Doc id MA-43265
--	---	----------------------------------

CCI

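### The secondary grade 0/1 responder rates have no prespecified check for subjects who exit, and the SAP has no rule for early-termination ratings

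*SAP*

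**What the plan says.** SAP 1.4.2 defines the first secondary endpoint as "Percentage of subjects who achieve a score of 0 or 1 at each post-treatment visit using the GL-ILA at maximum frown". The second is the matching LCL-ILA rate at maximum smile, requiring both sides.

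- **Missing data.** SAP 2.4.2 states that the secondary efficacy analysis "will be performed using the Observed Cases (OC), that is, no imputation will be done". Protocol 9.1.2.5 sets the same rule: "The Observed Cases (OC) will be used for all safety analyses as well as the secondary" efficacy analyses.
- **Denominator.** SAP 2.1: "Missing counts for all variables will be presented for informational purposes only and will not be included in percentage calculations".
- **Population and sensitivity analysis.** SAP 2.4.4: "The secondary analysis will be based on the ITT population with the remote visit assessments excluded". The one sensitivity analysis named there concerns visit type: "A sensitivity analysis will be conducted using the ITT population including the remote visit assessments". The table list agrees. Tables 14.2.3.1 and 14.2.3.2 (GL) and 14.2.4.1 and 14.2.4.2 (LCL) differ only in whether remote ratings count.
- **Discretion.** Protocol 9.1.2.5 adds: "If deemed necessary, any analyses may be repeated using OC, BOCF, or MI as appropriate". No trigger is given. In the SAP the sentence appears only in the safety section (2.5).
- **Early termination.** Subjects who withdraw are asked to complete the Month 6/ET assessments if possible (Protocol Table 2 footnote 2 and Section 5.5). These include both investigator scales (Protocol 8.1.7). SAP 2.1.1 tabulates data under the visit entered on the eCRF, even when out of window.

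The Month 1 primary endpoint, in contrast, has multiple imputation with a BOCF repeat.

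**The concern.** The later visits are where a response curve shows how long the effect lasts. Protocol 1.1 puts the usual duration of botulinum toxin type A in facial lines at roughly 4 to 6 months, which falls inside follow-up. Protocol 5.4.5 lists "Botulinum toxin of any serotype" among prohibited therapies, so a subject whose lines have returned cannot be retreated within protocol. Subjects may leave at any time (Protocol 5.5). It is therefore plausible, though nowhere shown, that some exits follow loss of effect.

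If so, observed-case rates at late visits describe those who stayed rather than those randomised, and the active arms look more durable than they are. A low placebo rate would move little, so the error would carry into the active-minus-placebo difference. Month 1, when cumulative exit is smallest, has a BOCF check; the later visits have none that is prespecified in the visible text.

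The ET visit adds a separate problem. A rating made well before Month 6 can be tabulated as Month 6 status.

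**Working it through.** **Figures in the documents.** Arm sizes are 118, 118, 118 and 59: 3 × 118 + 59 = 413, as stated. No late exit rate or late responder rate is given. The gap between 413 enrolled and 350 planned in the mITT population, 1 − 350/413 = 15.3%, is not an exit rate, because the mITT population excludes subjects with remote Month 1 ratings. Exit and response figures below are assumptions.

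**General form.** Let r be the rate at a visit among all subjects in an arm, d the proportion who have exited, and q the rate leavers would have had. Then r = (1−d)·OC + d·q, so

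OC − r = d(r − q)/(1 − d).

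- q = 0 (all leavers have lost response): OC = r/(1−d). The factor is 1.05, 1.11, 1.18 and 1.25 at d = 5%, 10%, 15% and 20%.
- q = r (exit unrelated to response): the difference is zero.
- q > r (leavers still responding): the sign reverses.

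**In percentage points.** For r from 20% to 50% and d from 5% to 20%:

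- q = 0: from 0.05 × 0.20/0.95 = 1.1 to 0.20 × 0.50/0.80 = 12.5 points.
- q = r/2: half of that, from 0.5 to 6.25 points.
- Placebo at an assumed r of 5%, q = 0, d = 20%: 0.20 × 0.05/0.80 = 1.25 points.

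**Example, one active arm of 118 with 35 responders among attenders and all leavers non-responders.**

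| Exited | Observed-case rate | Rate on 118 | Difference (points) |
|---|---|---|---|
| 6 | 35/112 = 31.2% | 29.7% | 1.6 |
| 12 | 35/106 = 33.0% | 29.7% | 3.4 |
| 18 | 35/100 = 35.0% | 29.7% | 5.3 |
| 24 | 35/94 = 37.2% | 29.7% | 7.6 |

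If the 18 leavers were all still responding, the rate on 118 would be (35 + 18)/118 = 44.9%, and observed cases at 35.0% would understate it.

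**Month 6 depends on the ET ratings.** With 18 exits and 35 responders among 100 attenders, the observed-case Month 6 rate is:

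| ET ratings entered under Month 6/ET | Rate |
|---|---|
| none | 35/100 = 35.0% |
| 9, all non-response | 35/109 = 32.1% |
| 18, all non-response | 35/118 = 29.7% |
| 18, all made while still responding | 53/118 = 44.9% |

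In the last row, if those 18 had lost response by Month 6, the correct figure would be 29.7%. That error comes from visit assignment and is not bounded by 1/(1−d). With a month defined as 28 days, Month 6 is day 168 ± 5. An ET rating on day 60 lies in the Month 2 window (day 56 ± 5), yet could stand as Month 6 status 108 days early.

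**The case against.** Several stronger readings are tempting, and the documents do not support them.

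- *Leavers vanish from every later visit, Month 6 included.* Not necessarily. They are asked for an ET rating, and one showing non-response under Month 6/ET would put them back in the denominator. This stands, and it shifts the Month 6 problem to the missing assignment rule.
- *A subject must leave in order to be retreated.* Protocol 5.4.5 does not say so: after a prohibited therapy the Medical Monitor is notified to discuss continuation. Exclusion criterion 2 also keeps out people who expect to need toxin during the study. No document shows that loss of effect drives exit.
- *Durability as a whole is left unprotected.* Kaplan-Meier analyses of time to return to baseline and time to loss of grade 0/1 are planned (Tables 14.2.14.1 to 14.2.17.2) and keep leavers at risk until censoring. They help only if censoring is unrelated to loss of effect, which is the assumption in doubt.

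Other points on this side are fair. The endpoints are descriptive (Protocol 9.1.5), and the secondary CMH tests are labelled so (SAP 2.4.4). Missing counts and discontinuation by visit will be reported, so a reader could rebuild much of a worst-case denominator. The shift may be smaller than sampling error: the exact interval for 35/100 is 25.7% to 45.2%, which contains 29.7%. Counting every exit as a failure also penalises relocation and schedule conflicts.

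Text after the observed-case sentence in SAP 2.4.2 and after 2.4.4 is blacked out, so the absence of another check can be asserted only for visible text. The numbering from 14.2.3.1 to 14.2.4.3 is unbroken, however, so no hidden table sits among those for these two endpoints.

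**Conclusion.** The point holds as a gap in sensitivity analysis, not as a demonstrated bias. Exited subjects are absent from numerator and denominator at the visits from exit to Month 5. At Month 6 they are either absent or represented by a rating that may be months old.

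If exit is related to loss of effect, omission overstates late active-arm rates by at most 1/(1−d): 1.05 at an assumed 5% exit and 1.25 at an assumed 20%. Both the exit rate and the response of leavers are assumptions, and the direction depends on the latter. A reader might infer that late persistence will be overstated; the documents establish only that it could be, with no prespecified analysis to show by how much.

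The Month 1 primary conclusion and its type I error control are untouched. The change is worth making because it is cheap and follows logic already in the SAP.

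**What to change.** Keep observed cases as the main secondary analysis and amend SAP 2.4.4 as follows.

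1. Prespecify one sensitivity repeat of Tables 14.2.3.1 and 14.2.4.1. A subject whose exit date precedes the visit's window stays in the denominator as a non-responder. For eligible subjects this matches the SAP's BOCF result, since baseline grade is 2 or 3. Single missed visits and remote-only visits stay as observed cases, so the repeat addresses exit only and should be labelled that way.
2. State that an ET rating is used only at the scheduled visit whose window contains its date, and is not otherwise counted as Month 6 status. If it falls between windows, it is listed only.
3. State that, for these two endpoints, this repeat replaces reliance on the discretionary clause in Protocol 9.1.2.5, and record the change in SAP 2.8.

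The cost is SAP wording, a little date-based programming and one rerun of two tables. Late active rates may look slightly lower in the repeat. Because exits unrelated to efficacy are scored as failures, it should remain a sensitivity analysis.

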2.4.3 Primary analysis

The primary efficacy endpoints will be the composite responder rate based on the GL-ILA and GL-SLA of GL severity at maximum frown at Month 1 (described in [Section 1.3.3](#) and [Section 1.3.4](#), respectively) as well as the composite responder rate based on the LCL-ILA and LCL-SLA of LCL severity at maximum smile at Month 1 (described in [Section 1.3.1](#) and [Section 1.3.2](#), respectively). To evaluate the effectiveness of QM1114-DP versus placebo in the treatment of moderate to severe LCL and GL, alone or in combination, the responder rates of the QM1114-DP and placebo will be compared using the Cochran-Mantel-Haenszel (CMH) test stratified by site at the 5% significance level (2-sided). The group treated in one rhytid area alone (the QM1114-DP in LCL/placebo in GL; the placebo in LCL/QM1114-DP in GL treatment groups) and the group with concurrent LCL and GL treatment (the QM1114-DP in LCL/QM1114-DP in GL treatment group) will be analyzed separately.

The null hypothesis of no relationship between treatment and responder rate will be tested against the alternative hypothesis that there is a relationship between treatment and responder rate. For a significant result, the two-sided p-value of the comparison of the composite GL-ILA/GL-SLA and composite LCL-ILA/LCL-SLA responder rates between the QM1114-DP treated and placebo treated subjects at Month 1 using the CMH test needs to be smaller than 0.05. The Breslow-Day test will be used to assess the homogeneity of the odds ratios across all sites.

To control the type I error rate among the 4 primary efficacy comparisons, the fixed sequence procedure will be used which requires no adjustment to the level of significance. The comparisons will be done in the following order:

1. GL alone group vs placebo on the **GL scale** (i.e. the placebo in LCL/QM1114-DP in GL group vs. the placebo in LCL/placebo in GL group)
2. GL + LCL group vs placebo on the **GL scale** (i.e. the QM1114-DP in LCL/QM1114-DP in GL group vs. the placebo in LCL/placebo in GL group)
3. LCL alone group vs placebo on the **LCL scale** (i.e. the QM1114-DP in LCL/placebo in GL group vs. the placebo in LCL/placebo in GL group)
4. GL + LCL group vs placebo on the **LCL scale** (i.e. the QM1114-DP in LCL/QM1114-DP in GL group vs. the placebo in LCL/placebo in GL group)

The estimates of the composite GL-ILA/GL-SLA and the composite LCL-ILA/LCL-SLA responder rates in each treatment group will be presented as well as the difference in responder rates (QM1114-DP responder rate – placebo responder rate). Corresponding 95% CI for the treatment group composite GL-ILA/GL-SLA and the LCL-ILA/LCL-SLA responder rates and the difference in responder rates along with the p-value for the difference will also be presented. The normal approximation (Wald) method will be used to calculate both the 95% CI for the individual treatment group composite GL-ILA/GL-SLA and LCL-ILA/LCL-SLA responder rates and the 95% CI for the difference in responder rates. The above responder rates will be presented in figures by visit and treatment group.

 GALDERMA	Title 43QMI902 Statistical Analysis Plan US - QM1114-DP - GL&LCL	Doc id MA-43265
--	---	----------------------------------

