1.1.2 Number of subjects and randomization

The study will screen approximately 454 male and female adults, 18 years of age and older, with moderate to severe glabellar lines at maximum frown and moderate to severe lateral canthal lines at maximum smile in up to 15 study sites in order to enroll 413 subjects. Following the screening process, eligible subjects will be randomized at the baseline visit (Day 0) in a 2:2:2:1 ratio to:

- 60 units QM1114-DP (60 units in the LCL and placebo in the GL, 118 subjects),
- 50 units QM1114-DP (50 units in the GL and placebo in the LCL, 118 subjects),
- 110 units QM1114-DP (60 units in the LCL and 50 units in the GL, 118 subjects), or
- Placebo in both the LCL and GL (59 subjects).

Randomization will be stratified by study center.

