2.4.3.2 Subgroup analysis

Additionally, to evaluate the consistency of the results of the primary analysis across different subgroups of interest, the primary analysis specified above ([Section 2.4.3](#)) will be repeated, stratifying for each of the following subgroups specified below:

- Age (less than 65 years old, 65+ years old)
- Gender (Male, Female; if enough males are recruited)
- Baseline severity score of the GL-ILA at maximum frown (Grade 2 (Moderate), Grade 3 (Severe))
- Baseline severity score of the LCL-ILA at maximum smile (Level 2 (Moderate), Level 3 (Severe, using the worst value from the right and left sides)).
- Prior botulinum toxin use (Yes, No)
- Fitzpatrick skin type (I-III, IV-VI)
- Site
- Type of Month 1 visit (Onsite, Remote)

For each subgroup, the responder rates, difference in responder rates between the treatment groups, and the corresponding 95% CI will be presented. The Breslow-Day test will be used to assess the homogeneity of the odds ratios across all the subjects within each subgroup. The subgroup analysis for type of Month 1 visit will be performed based on the ITT population.

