2.7.3 Sample size calculation

The study is planned to include approximately 350 subjects in the mITT population: 100 subjects will be treated with QM1114-DP, 200 subjects will be treated with QM1114-DP and placebo, and 50 subjects will be treated with placebo.

The sample size is determined by the number of subjects exposed to QM1114-DP in the LCL and GL, and amount of long-term safety data.

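### The primary responder rates and their difference get Wald intervals with no rule for sparse placebo counts, although the secondary rates get exact intervals

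*SAP*

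**What the plan says.** SAP 2.1 sets the level: "Confidence intervals (CI) and p-values will be 2-sided and performed at a significance level of 5%, unless otherwise specified". For the primary composite endpoints, SAP 2.4.3 then names the method: "The normal approximation (Wald) method will be used to calculate both the 95% CI for the individual treatment group" composite "responder rates and the 95% CI for the difference in responder rates". Nothing is said about zero or sparse counts.

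SAP 2.4.4 takes a different line for the secondary responder rates (grade 0 or 1 on the investigator scale alone): "The Clopper-Pearson (Exact) method will be used to calculate the CIs". Neither section explains the difference in method, and SAP 2.8 does not mention it.

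The Wald rule travels beyond the main table. SAP 2.4.3.1 repeats the 2.4.3 analysis with BOCF, with observed cases in the ITT population, and in the PP and Safety populations. SAP 2.4.3.2 repeats it within eight subgroup factors, one of which is site: "For each subgroup, the responder rates, difference in responder rates between the treatment groups, and the corresponding 95% CI will be presented".

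On size, SAP 1.1.2 says "eligible subjects will be randomized at the baseline visit (Day 0) in a 2:2:2:1 ratio to" the four groups, and SAP 2.7.3 says of the mITT population that "50 subjects will be treated with placebo".

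**The concern.** The Wald interval takes its width from the observed proportion. When that proportion is zero the estimated variance is zero and the interval has no width. When it is close to zero the interval is too narrow above and runs below zero. The composite endpoint makes low placebo counts foreseeable. SAP 1.4.1 requires grade 0 or 1 and at least two grades of improvement on both the investigator and the subject scale, and for LCL on both sides of the face. Protocol 1.3 expects no clinical benefit for the placebo group.

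The plan therefore applies the fragile method to the stricter endpoint and the robust one to the easier endpoint. At stake are the error bars in the primary efficacy tables: the stated precision of the placebo rate, and to a smaller extent the lower limit of the treatment difference.

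**Working it through.** **Inputs from the documents.** Two-sided 95% level (SAP 2.1); Wald for rates and difference (SAP 2.4.3); 2:2:2:1 allocation and up to 15 sites (SAP 1.1.2); 350 planned in mITT (SAP 2.7.3); 413 enrolled (SAP 2.7.1); five imputed data sets pooled through MIANALYZE (SAP 2.4.2).

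**Assumed, because the planning rates are redacted.** True placebo rates of 0.5% to 5%; 0 to 2 placebo responders for the difference; active rates of 30% to 90% for the limits and 40% to 90% for coverage. The Wald difference is taken in its usual unpooled form. Site stratification and imputation are not modelled.

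**Group sizes reproduced.** 350/7 = 50 placebo and 2 × 50 = 100 per active group; 413/7 = 59 placebo and 2 × 59 = 118 per active group. These match the SAP. The documents show no interval width or coverage to reproduce.

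**Placebo rate.** Wald is p ± 1.96 × √(p(1−p)/n). At 0/50 this is 0 ± 0. The Clopper-Pearson upper limit with zero responders is 1 − 0.025^(1/n): 7.1% for n = 50 and 6.1% for n = 59.

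| Responders of 50 | Wald | Clopper-Pearson |
|---|---|---|
| 0 | 0.0% to 0.0% | 0.0% to 7.1% |
| 1 | −1.9% to 5.9% | 0.1% to 10.6% |
| 2 | −1.4% to 9.4% | 0.5% to 13.7% |

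With one or two responders the Wald upper limit is 4.7 and 4.3 points below the exact one.

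**Coverage of the nominal 95% placebo interval, n = 50, by exact binomial enumeration.**

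| True rate | Chance of 0/50 | Wald | Wilson | Clopper-Pearson |
|---|---|---|---|---|
| 0.5% | 77.8% | 22.2% | 97.4% | 99.8% |
| 1% | 60.5% | 39.5% | 91.1% | 98.6% |
| 2% | 36.4% | 63.5% | 92.2% | 98.2% |
| 3% | 21.8% | 78.1% | 93.7% | 98.3% |
| 5% | 7.7% | 92.0% | 96.2% | 98.8% |

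In this range the Wald shortfall is almost entirely the chance of seeing no responders. At 1%, for example, 100 − 60.5 = 39.5.

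**Difference, 100 against 50.** Take 60/100 against 0/50.
- Wald: √(0.6 × 0.4/100 + 0) = 0.0490, so 60 ± 9.6 gives 50.4% to 69.6%.
- Newcombe lower limit: the Wilson lower limit for 60/100 is 50.2% and the Wilson upper limit for 0/50 is 7.1%, so 60 − √(9.8² + 7.1²) = 60 − 12.1 = 47.9%.
- Miettinen-Nurminen lower limit: 50.2%.

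Lower limits in percentage points, as Wald / Newcombe / Miettinen-Nurminen:

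| Active rate | 0 placebo responders | 1 | 2 |
|---|---|---|---|
| 30% | 21.0 / 19.2 / 21.9 | 18.2 / 16.3 / 17.3 | 15.5 / 13.5 / 14.2 |
| 60% | 50.4 / 47.9 / 50.2 | 47.6 / 45.0 / 46.3 | 45.0 / 42.4 / 43.4 |
| 90% | 84.1 / 79.7 / 82.3 | 81.0 / 76.7 / 78.0 | 78.0 / 74.0 / 75.0 |

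Over active rates of 30% to 90%, Wald is 1.8 to 4.4 points above Newcombe. Against Miettinen-Nurminen it runs from 0.9 below (30% active, no placebo responders) to 3.0 above (90% active, one or two).

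Across 24 scenarios (placebo 0.5%, 1%, 2%, 5%; active 40% to 90%), two-sided Wald coverage is 91.8% to 95.2%. The chance that the lower limit exceeds the true difference is nominally 2.5%. It is 2.2% to 7.3%, and above 2.5% in 22 of the 24.

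**By-site tables.** If 15 sites recruit equally, 50/15 is about 3.3 placebo subjects per site. At 0/3 Wald again gives 0% to 0%, while the exact upper limit is 1 − 0.025^(1/3) = 71%.

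**Multiple imputation.** Total variance is W + (1 + 1/5)B. If all five imputed sets have no placebo responders, the within part W and the between part B are both zero, so pooling does not restore any width to the placebo interval.

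**The case against.** The strongest reply is that no decision rests on these intervals. Success is judged by the site-stratified CMH p-value in a fixed sequence. A reader might infer that the primary conclusion or the type I error is at risk, and the documents do not support that. The smallest Wald lower limit in the grid is 15.5 points, and the smallest under the alternatives is 13.5, so zero is excluded every time. This stands and sets the weight of the point.

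Further limits also stand:
- **Zero as the usual placebo result.** Zero is the likeliest count only below a true rate of 1/51, about 2%. At 2%, one responder (37.2%) is already slightly likelier than none (36.4%). Protocol 1.3 speaks of clinical benefit and gives no response rate.
- **A lower limit that always favours the product.** With no placebo responders and an active rate of 50% or less, the Miettinen-Nurminen lower limit is slightly above Wald's. Part of the gap to Newcombe is Newcombe's own caution: its lower limit exceeds the true difference at most 1.44% of the time in the same scenarios.
- **Imputation always collapsing.** This needs zero placebo responders in all five sets and affects only the placebo rate. The difference keeps its active-arm variance.
- **An unstratified interval beside a stratified test.** Reporting a marginal difference is a legitimate choice, and no numerical harm has been shown.
- **By-site counts.** SAP 2.1.2 pools sites into regions if any site enrols fewer than 5 subjects. That is conditional: equal recruitment of 413 over 15 sites gives about 27 per site and would not trigger it.

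None of this defends a zero-width 95% interval in a primary table, or explains why the secondary endpoint gets the better method.

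**Conclusion.** The point holds as a defect of precision and reporting that should be fixed. It is clearest for the placebo rate: no width at zero responders, an upper limit 4 to 5 points too low with one or two, and coverage from 22% to 92% over assumed true rates of 0.5% to 5%. Those coverage figures describe the placebo interval and should not be read as describing the treatment effect.

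For the difference the effect is modest. The Wald lower limit is usually, though not always, too favourable, and most so at high active rates. The same rule carries into the sensitivity and subgroup tables, where placebo counts may be much smaller. All sizes depend on responder rates that the public documents do not show. If the true placebo rate were 5% or more, a zero count would be unlikely (7.7% or less at n = 50) and the problem would be milder, though not absent.

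**What to change.** In SAP 2.4.3, and where it is reused in 2.4.3.1 and 2.4.3.2:

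- Replace Wald for single-group responder rates with Clopper-Pearson, which matches SAP 2.4.4, or with Wilson. Clopper-Pearson is the safer choice at very low rates; Wilson falls to 91.1% coverage at a true rate of 1%.
- Replace Wald for the difference with Miettinen-Nurminen or Newcombe, and name the one chosen.
- For the imputed analysis, write down a pooling rule, because exact limits cannot be combined directly through MIANALYZE. One option is a Wilson-type interval built on the Rubin-pooled proportion, with the two arms combined in Newcombe's manner. The rule should say what happens when no imputed set has a placebo responder.
- A site-stratified interval to sit beside the CMH test is optional.

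The cost is a few sentences in the SAP, slightly wider intervals, and a different procedure option for the tables without imputation. The imputation step needs a little extra programming. The CMH test, the fixed sequence and the sample size do not change.
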